15.4.2 Secondary Performance

The secondary effectiveness endpoints are:

- Monocular distance corrected near visual acuity at 40 cm
- Proportion of subjects who respond “Never” to Q1 of the IOLSAT questionnaire: “Overall, in the past 7 days, how often did you need to wear eyeglasses to see?”
- Monocular uncorrected intermediate visual acuity at 66 cm
- Monocular uncorrected distance visual acuity

15.4.2.1 Statistical Hypotheses

The statistical hypothesis in support of the first secondary effectiveness objective is:

- ACRYSOF IQ EDF IOL is superior to ACRYSOF IQ Monofocal IOL with respect to mean monocular photopic distance corrected near visual acuity (40 cm from spectacle plane) at Visit 4A (120-180d postoperative)

The null and alternative hypotheses for the first secondary analysis are:

$$H_0: \mu_{DFT015VA} \geq \mu_{SN60WFVA}$$

$$H_A: \mu_{DFT015VA} < \mu_{SN60WFVA}$$

where $\mu_{DFT015VA}$ and $\mu_{SN60WFVA}$ refer to the mean monocular photopic DCNVA at 40 cm for the test and control lenses, respectively, in the first implanted eye. Second implanted eye analysis will be supportive.

The statistical hypothesis in support of the second secondary effectiveness objective is:

- ACRYSOF IQ EDF IOL is superior to ACRYSOF IQ Monofocal IOL with respect to proportion of subjects who respond “Never” to Q1 of the IOLSAT questionnaire (Overall, in the past 7 days, how often did you need to wear eyeglasses to see?) at Visit 4A (120-180d postoperative).

The null and alternative hypotheses for the second secondary analysis are:

$$H_0: \pi_{DFT015Q1} \leq \pi_{SN60WFQ1}$$

$$H_A: \pi_{DFT015Q1} > \pi_{SN60WFQ1}$$

where $\pi_{DFT015Q1}$ and $\pi_{SN60WFQ1}$ refer to the proportion of subjects who responded “Never” for the test and control lenses.

There are no hypothesis tests associated with the third and the fourth secondary effectiveness endpoints (UCIVA and UCDVA, respectively).

15.4.2.2 Analysis Methods

Analysis of first secondary effectiveness endpoint (DCNVA) will be based on a two-sample t-test, with a type I error rate of 2.5%, 1-sided. The difference in means (ACRYSOF IQ EDF IOL minus ACRYSOF IQ Monofocal IOL) and the associated two-sided 95% confidence interval will be presented.

Two performance targets in support of the first secondary effectiveness objective are:

- At least 50% of eyes with ACRYSOF IQ EDF IOL achieve a monocular DCNVA of 0.3 logMAR or better
- The percentage of eyes with DCNVA of 0.3 logMAR or better in ACRYSOF IQ EDF IOL group is at least 25 percentage points higher than in ACRYSOF IQ Monofocal IOL group.

For the first performance target, the percentage of eyes achieving distance corrected near visual acuity of 0.3 logMAR or better in ACRYSOF IQ EDF IOL group will be presented and compared against the performance target of 50%. For the second performance target, the percentage of eyes achieving distance corrected near visual acuity of 0.3 logMAR or better in each IOL group will be presented and the difference between the IOL groups (ACRYSOF IQ EDF IOL – ACRYSOF IQ Monofocal IOL) will be compared against the performance target of 25%.

A success on the first secondary effectiveness endpoint will be indicated by successful outcomes on the hypothesis test and two performance targets. A hypothesis test on the second secondary effectiveness endpoint will be conducted only after successful outcomes on the first secondary endpoint are demonstrated.

For the second secondary effectiveness endpoint, a two-sided 95% confidence interval for the difference in proportions (ACRYSOF IQ EDF IOL – ACRYSOF IQ Monofocal IOL) will be calculated using the Miettinen-Nurminen method (1985), and ACRYSOF IQ EDF IOL will be determined to be superior to ACRYSOF IQ Monofocal IOL if the lower boundary of the confidence interval is greater than zero. This is equivalent to using a type I error rate of 2.5%, 1-sided.

If IOLSAT questionnaire generates scores, the cumulative distribution curves showing the percentage of subjects with a given change in their score compared to baseline by IOL group will be presented to help determine whether any observed differences are meaningful.

In addition, the frequencies of each item in IOLSAT will be summarized by visit with counts and percentages.

For the third and the fourth secondary effectiveness endpoints (UCIVA and UCDVA, respectively), the following descriptive statistics will be provided for each IOL group:

- The number and percentage of eyes with visual acuity of
 - 0.0 logMAR or better: ≤ 0.00 logMAR
 - 0.1 logMAR or better: ≤ 0.10 logMAR
 - 0.2 logMAR or better: ≤ 0.20 logMAR
 - 0.3 logMAR or better: ≤ 0.30 logMAR
- Descriptive statistics including mean, median, standard deviation, number of eyes, minimum, maximum and (two-sided) 95% confidence interval will be presented for overall, by preoperative corneal cylinder (≤ 0.5 D vs. > 0.5 D), and by residual corneal cylinder (≤ 0.5 D vs. > 0.5 D).

In addition, the difference in means (ACRYSOF IQ EDF IOL minus ACRYSOF IQ Monofocal IOL) and the associated two-sided 95% confidence interval will be presented.

First implanted eyes and second implanted eyes assessments will be in separate tables.

A horizontal bar chart consisting of 20 solid black bars of varying lengths. The bars are arranged in two main groups: a top group of 10 bars and a bottom group of 10 bars. The bars in the top group are generally longer than those in the bottom group. The bars are separated by small gaps and are set against a white background.

Visual Acuity Endpoints

In general, for visual acuity endpoints, the following descriptive statistics will be provided for each IOL group:

- The number and percentage of eyes with visual acuity of
 - 0.0 logMAR or better: ≤ 0.00 logMAR
 - 0.1 logMAR or better: ≤ 0.10 logMAR
 - 0.2 logMAR or better: ≤ 0.20 logMAR
 - 0.3 logMAR or better: ≤ 0.30 logMAR
- Descriptive statistics including sample size, mean, median, standard deviation, number of eyes, minimum, maximum and the confidence interval will be presented.

Additionally, these descriptive statistics will be provided for the first two co-primary and the first secondary visual acuity endpoints, for first eye and second eye, by age categories (<65 years vs. ≥ 65 years), by investigative site, by adverse event (study eyes with ocular adverse events vs. study eyes without ocular adverse events) and by preoperative ocular pathology (study eyes with vs. study eyes without) for both the AAS and BAS. Listings of these visual acuity endpoints at every visit for each eye will also be provided.

In addition, the difference in means (ACRYSOF IQ EDF IOL minus ACRYSOF IQ Monofocal IOL) and the associated two-sided 95% confidence interval will be presented.

First implanted eyes, second implanted eyes [REDACTED] will be in separate tables.

Defocus curve evaluation at Visit 4A (120-180d postoperative)

Descriptive statistics (mean, median, standard deviation, number of eyes/subjects, minimum, maximum, and two-sided 95% confidence intervals) will be provided for the logMAR VA measured on the ETDRS chart at each defocus level for all eyes/subjects. The mean logMAR VA measured on the ETDRS chart at each defocus value will be displayed graphically for all eyes/subjects, separately for first implanted eye, second implanted eye and binocular assessments. Mean logMAR visual acuity will be plotted versus defocus value, including two-sided 95% confidence intervals and standard deviations, with the amount of defocus along the x-axis and logMAR VA at each defocus point along the y-axis. The defocus tables and plots will be generated overall and by site.

In addition, monocular defocus curves for the first implanted eye and second implanted eye will be presented, by treatment group, for the following photopic pupil ranges: [<3.0 mm (small), ≥3.0 mm to ≤4.0 mm (medium), and >4.0 mm (large)] and three axial length ranges [<21.0 mm (short), ≥21.0 mm to ≤26.0 mm (medium), and >26.0 mm (long)].

Manifest refraction

Descriptive statistics (number of eyes, mean, median, standard deviation, minimum, and maximum) on manifest refraction spherical equivalent (MRSE= sphere + $\frac{1}{2}$ cylinder) will be provided by IOL group.

First implanted eyes and second implanted eyes will be in separate tables.

1. **What is the primary purpose of the study?**

A horizontal bar chart with three bars of increasing height from left to right, representing data values of approximately 10, 20, and 30.

For more information, contact the Office of the Vice President for Research and Economic Development at [contact] or [contact].

For more information, contact the Office of the Vice President for Research and Economic Development at [contact] or [contact].

113
114
115

A thick black horizontal bar with a thin white horizontal line running through its center.

[REDACTED]

© 2019 Pearson Education, Inc.

A high-contrast, black and white image showing a series of horizontal bars of varying lengths. The bars are mostly black on a white background. In the lower portion of the image, there are several thick, black, stepped horizontal bars that create a stepped, architectural effect. A small white rectangular notch is visible on the left side of the second bar from the bottom. The bars are arranged in a descending order of length from top to bottom, with the stepped bars at the bottom.

15.5 Handling of Missing Data

The AAS and BAS do not include any imputed values. Although missing data will occur, the influence of missing data is expected to be minimal. The following sensitivity analyses will be conducted to address missing values for the first two co-primary effectiveness endpoints and first secondary effectiveness endpoint.

[figure not shown]
1. Multiple imputation with a fully conditional specification method will be used to impute and estimate the treatment effect.

2. The sensitivity of inferences to departures from the MAR assumption will be examined using a pattern-mixture model approach with a control-based pattern imputation (Ratitch 2011).

The details will be described in the Statistical Analysis Plan.

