If the QUVID questionnaire generates scores, the cumulative distribution curves showing the

percentage of subjects with a given change in their score compared to baseline by IOL group will be presented to help determine whether any observed differences are meaningful.

Counts and percentages of subjects who did not have a given visual disturbance at baseline but developed and present at Visit 4A (120-180d postoperative) will be presented.

In addition, the presence and absence of these symptoms, and how frequent, severe, and bothersome they appear will be summarized by visit with counts and percentages.

Sample Size Justifications

Approximately 220 subjects will be randomized to achieve 200 subjects who complete the study.

Effectiveness

The proposed sample size (N = 200; 100 for each IOL group) provides >99% power for the superiority hypothesis test on mean monocular photopic distance corrected intermediate visual acuity (66 cm) when tested at the 2.5% level of significance (one-sided). This assessment assumes:

Difference in DCIVA (66 cm) [logMAR]: Mean (SD) = -0.12 (0.18)

The proposed sample size will provide 84% power for the non-inferiority hypothesis with respect to mean photopic monocular best corrected distance visual acuity when tested at the 5% level of significance (one-sided) with a non-inferiority margin of 0.1 logMAR assuming:

Difference in BCDVA [logMAR]: Mean (SD) = 0.04 (0.16)

The proposed sample size provides >99% power for the superiority hypothesis test on mean photopic monocular distance corrected near visual acuity (40 cm) when tested at the 2.5% level of significance (one-sided). This assessment assumes:

Difference in DCNVA (40 cm) [logMAR]: Mean (SD) = -0.12 (0.18)

The proposed sample size will provide 94% power, with $\alpha=2.5\%$, 1-sided, to detect a difference of 25% in proportion of subjects who respond “Never” to Q1 of the IOLSAT questionnaire (Overall, in the past 7 days, how often did you need to wear eyeglasses to see?), assuming a 50% rate in the ACRYSOF IQ EDF IOL group.

Adverse Events

For any event where zero incidence is observed in 100 operative eyes with ACRYSOF IQ EDF IOL, the one-sided exact 95% upper confidence limit is less than 3%. Thus, with 95% confidence the true adverse event rate is less than 3%.

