15.4.1.1 Statistical Hypotheses

The statistical hypotheses in support of the primary effectiveness objectives are:

- ACRYSOF IQ EDF IOL is superior to ACRYSOF IQ Monofocal IOL with respect to mean monocular photopic distance corrected intermediate visual acuity (66 cm from spectacle plane) at Visit 4A (120-180d postoperative)

The null and alternative hypotheses for the first co-primary analysis are:

$$H_0: \mu_{DFT015VA} \geq \mu_{SN60WFVA}$$
$$H_A: \mu_{DFT015VA} < \mu_{SN60WFVA}$$

where $\mu_{DFT015VA}$ and $\mu_{SN60WFVA}$ refer to the mean monocular photopic DCIVA at 66 cm for the test and control lenses, respectively, in the first implanted eye. Second implanted eye analysis will be supportive.

- ACRYSOF IQ EDF IOL is non-inferior compared to ACRYSOF IQ Monofocal IOL with respect to mean monocular photopic best corrected distance visual acuity at Visit 4A (120-180d postoperative). The non-inferiority margin will be 0.1 logMAR.

The null and alternative hypotheses for the second co-primary endpoint are:

$$H_0: \mu_{DFT015VA} - \mu_{SN60WFVA} \geq \Delta$$
$$H_A: \mu_{DFT015VA} - \mu_{SN60WFVA} < \Delta$$

where Δ refers to the non-inferiority margin, set at 0.10 logMAR, and $\mu_{DFT015VA}$ and $\mu_{SN60WFVA}$ refer to the mean monocular photopic BCDVA for the test and control lenses, respectively, in the first implanted eye. Second implanted eye analysis will be supportive.

Two performance targets in support of the primary effectiveness objectives are:

- Monocular mean defocus curve for ACRYSOF IQ EDF IOL has a range of defocus at least 0.5 D greater negative range than ACRYSOF IQ Monofocal IOL at 0.2 logMAR at Visit 4A (120-180d postoperative).
- ACRYSOF IQ EDF IOL has at least 50% of eyes achieving monocular photopic distance corrected intermediate vision of 0.2 logMAR or better at Visit 4A (120-180d postoperative).

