15.4.1.2 Analysis Methods

Analysis of the first primary effectiveness endpoint (DCIVA) will be based on a two-sample t-test, with a type I error rate of 2.5%, 1-sided. The difference in means (ACRYSOF IQ EDF IOL minus ACRYSOF IQ Monofocal IOL) and the associated two-sided 95% confidence interval will be presented.

Analysis of the second primary effectiveness endpoint (BCDVA) will be based on a two-sample t-test, with a type I error rate of 5%, 1-sided. The difference in means (ACRYSOF IQ EDF IOL minus ACRYSOF IQ Monofocal IOL) and the associated one-sided 95% upper confidence limit will be presented.

Data poolability will be analyzed by testing a treatment by site interaction effect: first, the interaction effect between treatment and site will be tested using an alpha of 0.15; second, if the interaction effect is found significant, the final analysis model will include site as a random effect.

For the first performance target (depth of focus), the line plot of the average visual acuity at each defocus level (ie, defocus curve) will be used to estimate the negative lens induced depth of focus at 0.2 logMAR. The difference in the depth of focus between ACRYSOF IQ EDF IOL and ACRYSOF IQ Monofocal IOL will be presented. The following sensitivity analyses will be performed on the depth of focus endpoint:

- Exclude extreme outliers (individual depth of focus values less than $Q1 - 3*IQR$ or greater than $Q3 + 3*IQR$)

- Exclude mild outliers (individual depth of focus values less than $Q1 - 1.5 \times IQR$ or greater than $Q3 + 1.5 \times IQR$), where $Q1 = 25$ th percentile, $Q3 = 75$ th percentile, and $IQR = Q3 - Q1$.

The depth of focus data will be presented by IOL group, 3 photopic pupil size ranges [<3.0 mm (small), ≥ 3.0 mm to ≤ 4.0 mm (medium), and >4.0 mm (large)] and three axial length ranges [<21.0 mm (short), ≥ 21.0 mm to ≤ 26.0 mm (medium), and >26.0 mm (long)].

Descriptive summary statistics (number of eyes, mean, median, standard deviation, minimum, and maximum) on individual depth of focus value will be presented by IOL group.

For the second performance target (DCIVA), the percentage of eyes achieving distance corrected intermediate visual acuity of 0.2 logMAR or better in each IOL group will be presented.

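### If the test lens is worse on BCDVA, control-based imputation eases the non-inferiority test, and it is the only not-at-random check that section 15.5 names

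*Protocol*

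**What the plan says.** Protocol section 15.5 keeps imputation out of the main analyses ("The AAS and BAS do not include any imputed values") and lists two sensitivity analyses "for the first two co-primary effectiveness endpoints and first secondary effectiveness endpoint", that is, for DCIVA, BCDVA and DCNVA.

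- The first works under missing at random (MAR): "Multiple imputation with a fully conditional specification method will be used to impute and estimate the treatment effect".
- The second is the only one aimed at data not missing at random: "The sensitivity of inferences to departures from the MAR assumption will be examined using a pattern-mixture model approach with a control-based pattern imputation".

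Details are left to the SAP. The section does not separate the superiority endpoints (DCIVA, DCNVA) from the non-inferiority endpoint (BCDVA).

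For BCDVA, section 15.4.1.1 fixes the margin: "The non-inferiority margin will be 0.1 logMAR". The difference is test minus control, and a higher logMAR is worse. Section 15.4.1.2 tests at one-sided 5%, with the "associated one-sided 95% upper confidence limit will be presented". The synopsis plans for a test lens that is slightly worse, by 0.04 logMAR with SD 0.16, and says: "The proposed sample size will provide 84% power for the non-inferiority hypothesis".

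**The concern.** Control-based imputation draws missing test-lens outcomes from the control-lens model and so pulls the arms together. In a superiority test that removes benefit, which makes it a fair stress. In a non-inferiority test with a deficit it removes part of the deficit, so the criterion becomes easier to meet.

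The relevant not-at-random question for BCDVA is whether non-inferiority would hold if test-lens eyes without a Visit 4A measurement did worse than those measured. The named method never poses that question. The fully conditional specification analysis is neutral in direction and does not pose it either.

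BCDVA is also the co-primary hypothesis test with less room: 84% stated power, against more than 99% for DCIVA. A reader could take a favourable control-based result as reassurance when it comes partly from the method.

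**Working it through.** **Inputs from the protocol.** Margin 0.10 logMAR (15.4.1.1); one-sided 5% (15.4.1.2); difference 0.04, SD 0.16 and 100 eyes per arm (synopsis, Sample Size Justifications). Section 10 plans 220 randomized and 200 completing, so 10 of 110 eyes missing per arm. That is an upper end, because section 10 counts losses from randomization while the all-implanted set (15.2) holds only successfully implanted eyes.

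**Assumptions.** A lower case of 5 of 105 missing per arm; data missing at random; one earlier BCDVA visit carrying the same deficit, with correlation r of 0.5 or 0.7 to Visit 4A; no added shift in the control-based method.

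**The plan's own figure.** SE = 0.16 × √(2/100) = 0.0226. Noncentrality = (0.10 − 0.04)/0.0226 = 2.65 on 198 df, giving 84.1% power. The stated 84% reproduces.

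**Size of the pull.** With a share f of test-lens eyes missing and a true difference d, control-based imputation moves the expected estimate toward zero by f × d × (1 − r). At d = 0.04:

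| Missing per arm | No earlier acuity (r = 0) | r = 0.5 | r = 0.7 |
|---|---|---|---|
| 10 of 110 | 0.0036 | 0.0018 | 0.0011 |
| 5 of 105 | 0.0019 | 0.0010 | 0.0006 |

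In the first cell the estimate falls from 0.0400 to 0.0364. With equal lenses the shift is nil. With a better test lens it works against that lens: in 3,000 simulated trials at a true −0.02, with 10 missing and no earlier acuity, −0.021 under MAR became −0.019.

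**Chance that the sensitivity analysis meets the criterion.** 20,000 simulated trials per row, 20 imputations, Rubin's rules, upper limit against 0.10. The last column adds 0.10 logMAR to imputed test-lens values.

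True difference 0.04:

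| Missing | Earlier BCDVA | Control-based | MAR | MAR + 0.10 |
|---|---|---|---|---|
| 10 | none | 89.9% | 83.9% | 71.6% |
| 10 | r = 0.5 | 87.5% | 83.9% | 72.2% |
| 10 | r = 0.7 | 87.8% | 85.7% | 74.4% |
| 5 | none | 86.5% | 83.6% | 77.7% |
| 5 | r = 0.5 | 86.3% | 84.6% | 78.6% |
| 5 | r = 0.7 | 85.7% | 84.5% | 78.7% |

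Control-based imputation passes 1.2 to 6.0 points more often than MAR. A worsening shift moves the rate the other way.

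True difference 0.10, at the margin:

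| Missing | Earlier BCDVA | Control-based | Observed cases |
|---|---|---|---|
| 10 | none | 8.5% | 5.1% |
| 10 | r = 0.5 | 6.0% | 4.9% |
| 10 | r = 0.7 | 5.4% | 5.0% |
| 5 | none | 6.3% | 4.9% |
| 5 | r = 0.5 | 5.5% | 5.1% |
| 5 | r = 0.7 | 5.5% | 5.3% |

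Simulation error here is about 0.15 points, so the smallest gaps are close to noise. These are pass rates of a supportive analysis, not error rates of the trial.

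**What a tipping point would show.** For a shift δ in imputed test-lens eyes and N eyes per arm including those missing, the upper limit without earlier acuity is about d + fδ + 1.653 × √(0.0226² + f(1 − f)δ²/N).

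- Observed 0.04: the limit is 0.04 + 1.653 × 0.0226 = 0.077 at δ = 0. At δ = 0.10 it is 0.087 (10 missing) or 0.082 (5 missing). It reaches 0.10 at δ = 0.233 or 0.419; modelling earlier acuity raises these to at most 0.241 and 0.426.
- Observed 0.06: the limit is already 0.097. It reaches 0.10 at about δ = 0.03 to 0.04 (10 missing) or 0.05 to 0.06 (5 missing).

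**The case against.** The case against is mostly about weight.

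- **Deferral.** Section 15.5 leaves details to the SAP, which could add a shift or a tipping point without contradicting the protocol. That is true. But section 15.5 itself chooses the method and assigns it to BCDVA, and it is that stated choice which does not suit the endpoint.
- **No decision depends on it.** Success rests on the four co-primary outcomes, and the BCDVA test uses no imputed values. This stands in full.
- **Size.** The pull is at most 0.0036 logMAR at the planned difference, under 4% of the margin. The 8.5% figure needs both upper-end missingness and a model that ignores earlier acuity. With one earlier visit modelled, the excess over observed cases is 0.2 to 1.1 points. This also stands.
- **Sign.** The method is lenient only when the test lens is worse. That is right, and the point is limited to that case, which is the one the protocol plans for.
- **Little to learn.** At an observed 0.04 the tipping point is two to four times the margin, and at 0.06 the observed upper limit of 0.097 already shows fragility. In the first case, though, the tipping point would document real robustness. In the second it would say how small a shift overturns the result, while control-based imputation would move the estimate the reassuring way.

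**Conclusion.** The point holds as a minor one, worth considering. As named in section 15.5, neither sensitivity analysis tests BCDVA in the adverse direction, and the one meant for departures from MAR moves a deficit toward zero.

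At the planned 0.04 deficit the pull is 0.0006 to 0.0036 logMAR, worth 1.2 to 6.0 points in pass rate against MAR imputation. The range rests on 5 to 10 missing eyes per arm, the assumed correlations of 0 to 0.7 with earlier acuity, and control-based imputation without an added shift. The primary BCDVA result and type I error are untouched. The SAP may already supply a suitable analysis.

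**What to change.** In section 15.5, name a delta-adjusted tipping-point analysis as the not-at-random check for BCDVA. Impute missing test-lens eyes under MAR using earlier BCDVA (Visits 2 and 3A, and Early Exit where available). Worsen those imputed values in steps that include +0.10 logMAR, and continue until the upper limit reaches 0.10. Report the shift at which that happens and say whether it is plausible. Keep control-based imputation for DCIVA and DCNVA; for BCDVA it may stay as a supplement. Step sizes and the imputation model can go in the SAP.

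The cost is one sentence and a little programming. Sections 12.2.5 and 12.2.6 already collect BCDVA at the earlier visits, and section 12.3 recommends it at early exit, so no new data are needed. The drawback for the sponsor is that the BCDVA robustness result may look less favourable than under control-based imputation.
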